9.5 Missing data

Every effort will be undertaken to minimize missing data. The following approach to handling missing data will be adopted based on the type of the outcome and endpoint being analyzed.

Kaplan-Meier estimates will censor incomplete data at the last date of available follow-up information, assuming complete reporting of all events up to that date and event status unknown after that date.

9.6 Calculating days to event

When calculating the days-to-event, the date the event took place will always be compared to the index procedure date, also in case a staged procedure took place.

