8.7 Staged procedures

If the patient requires a staged procedure, this should be documented at the time of the index procedure, and must not be in the same epicardial vessel as any index lesion, and must not occur more than 45 days post-index procedure. The patient should receive the same type study stent as during the original index procedure (MISTENT or XIENCE).

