12.4 Clinical Event Committee (CEC)

The Clinical Events Committee (CEC) is an independent committee comprised of interventional cardiologists who are not participants in the study. The CEC is responsible for the categorization of Death, MI, revascularization and stent thrombosis, based on the definitions in the protocol. Prior to any CEC activity, a CEC Charter will be developed, which will describe the events to be adjudicated, the minimum amount of data required, and the algorithm followed in order to classify the events.

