Stent thrombosis should be reported as a cumulative value at the different time points and with the different separate time points. Time 0 is defined as the time point after the guiding catheter has been removed and the subject left the catheterization lab.

Timing:

- Acute stent thrombosis*: 0 - 24 hours post stent implantation
- Subacute stent thrombosis*: >24 hours - 30 days post stent implantation
- Late stent thrombosis†: 30 days - 1 year post stent implantation
- Very late stent/ thrombosis†: >1 year post stent implantation

* Acute/subacute can also be replaced by early stent thrombosis. Early stent thrombosis (0 - 30 days) - this definition is currently used in the community.

† Including “primary” as well as “secondary” late stent thrombosis; “secondary” late stent thrombosis is a stent thrombosis after a target segment revascularization.

Categories:

- Definite
- Probable
- Possible

Definitions of each category are as follows.

- **Definite stent thrombosis**

Definite stent thrombosis is considered to have occurred by either angiographic or pathologic confirmation.

Angiographic confirmation of stent thrombosis*

The presence of a thrombus[†] that originates in the stent or in the segment 5 mm proximal or distal to the stent and presence of at least one of the following criteria within a 48-hour time window:

- Acute onset of ischemic symptoms at rest
- New ischemic ECG changes that suggest acute ischemia
- Typical elevation or depression in cardiac biomarkers (refer to definition of spontaneous MI)
- Nonocclusive thrombosis
 - Thrombus Intracoronary thrombus is defined as a (spheric, ovoid, or irregular) noncalcified filling defect or lucency surrounded by contrast material (on 3 sides or within a coronary stenosis) seen in multiple

projections, or persistence of contrast material within the lumen, or a visible embolization of intraluminal material downstream.

- Occlusive thrombus
 - TIMI 0 or TIMI 1 in-stent or proximal to a stent up to the most adjacent proximal side branch or main branch (if originates from the side branch).
- * The incidental angiographic documentation of stent occlusion in the absence of clinical signs or symptoms is not considered a confirmed stent thrombosis.
- † Intracoronary thrombus.

Pathological confirmation of stent thrombosis

Evidence of recent thrombus within the stent determined at autopsy or via examination of tissue retrieved following thrombectomy.

- **Probable stent thrombosis**

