Either of the following occurred after stent implantation will be considered a probable stent thrombosis:

- Any unexplained death within the first 30 days[‡]
- Irrespective of the time after the index procedure, any MI that is related to documented acute ischemia in the territory of the implanted stent without angiographic confirmation of stent thrombosis and in the absence of any other obvious cause

‡ For studies with ST-elevation MI population, one may consider the exclusion of unexplained death within 30 days as evidence of probable stent thrombosis.

- **Possible stent thrombosis**

Clinical definition of possible stent thrombosis is considered to have occurred with any unexplained death from 30 days following intracoronary stenting until end of trial follow up.

STROKE

[Cerebrovascular Accident (CVA) / Stroke]

Stroke is defined as a sudden onset of focal neurological deficits due to vascular lesions of the brain that persists >24 hours. Any neurological symptom that lasts < 24 hours is classified as transient ischemic attack (TIA). Stroke results from either of two types of cerebral vascular disturbance: ischemia or hemorrhage.

[Transient ischemic attack (TIA)]

TIA are focal neurologic abnormalities of sudden onset and brief duration (i.e., lasting less than 24 hours) that reflect dysfunction in the distribution of the affected artery. TIAs include transient monocular blindness (e.g., amaurosis fugax defined as a transient episode of monocular blindness, or partial blindness, lasting ten minutes or less) and transient hemispheric attacks.

TIMI FLOW GRADES

0. No contrast flow through the stenosis.
1. A small amount of contrast flows through the stenosis but fails to fully opacify the artery beyond.
2. Contrast material flows through the stenosis to opacify the terminal artery segment. However, contrast enters the terminal segment perceptibly more slowly than more proximal segments. Alternatively, contrast material clears from a segment distal to a stenosis noticeably more slowly than from a comparable segment not preceded by a significant stenosis.
3. Anterograde flow into the terminal coronary artery segment through a stenosis is as prompt as anterograde flow into a comparable segment proximal to the stenosis. Contrast material clears as rapidly from the distal segment as from an uninvolved, more proximal segment.

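### Does counting every event from the index procedure misclassify stent thrombosis in staged stents?

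*Combined protocol and SAP*

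**What the plan says.** Three rules bear on the point.

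- **Time axis.** Section 9.6 sets the origin for days-to-event: "the date the event took place will always be compared to the index procedure date, also in case a staged procedure took place". It follows section 9.5, which gives the censoring rule for Kaplan-Meier estimates. Section 9.3 applies Kaplan-Meier to all clinical endpoints.
- **ST definitions.** Appendix II fixes acute, subacute, late and very late ST relative to implantation; late ST, for example, is "30 days - 1 year post stent implantation". Its time zero is when the patient leaves the catheterisation laboratory, and acute and subacute ST separate at 24 hours. Probable ST includes "Any unexplained death within the first 30 days", and possible ST is "any unexplained death from 30 days following intracoronary stenting until end of trial follow up". On reporting it says: "Stent thrombosis should be reported as a cumulative value at the different time points and with the different separate time points".
- **Who classifies.** Under section 12.4 the event committee is "responsible for the categorization of Death, MI, revascularization and stent thrombosis, based on the definitions in the protocol", with the algorithm left to a charter.

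Section 8.7 permits a planned staged procedure with the same type of study stent, which "must not occur more than 45 days post-index procedure". Section 6.2 lists the ST timing classes (5a), the definite, probable and possible categories (5b) and definite/probable ST combined (5c) as secondary endpoints.

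**The concern.** The 45-day staging limit lies beyond the 30-day boundary between early and late ST. If section 9.6 governed the ST class as well as the event time, every early ST of a stent placed after day 30 would be labelled late, and some early STs of stents placed sooner would be too. Near one year, some late events would become very late. An unexplained death soon after a staged stent could move from probable to possible ST and so drop out of the definite/probable count.

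Section 9.6 says always, names staging and exempts no endpoint. Appendix II does not say whether its time zero belongs to the index or the staged procedure. ST is a low-count safety result, so a single relabelled event would be visible.

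**Working it through.** The plan gives no figure on this point to reproduce. The check is to apply both clocks, see which the text assigns to ST class, and then size the effect if the wrong one were used.

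**1. Do the clocks differ?** Yes, for staged stents.

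| Staged stent placed | Event | Day from index | Label by index count | Label by implantation |
|---|---|---|---|---|
| Day 20 | ST 15 days later | 20 + 15 = 35 | late | subacute |
| Day 45 | ST 10 days later | 45 + 10 = 55 | late | subacute |
| Day 45 | ST 321 to 365 days later | 366 to 410 | very late | late |
| Day 45 | Unexplained death 20 days later | 45 + 20 = 65 | possible ST | probable ST |

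**2. Which clock sets the class?**

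- Section 12.4 makes categorisation the committee's task under the protocol definitions. For ST, those definitions are in Appendix II.
- Appendix II has its own time zero and a 24-hour limit. Section 9.6 compares a date with a date, which cannot reliably apply a 24-hour limit even in an unstaged patient. It therefore cannot be the rule for the full ST classification.
- The heading of 9.6 and its place after the censoring rule fit a rule for event times. A single patient-level origin, the same in both arms, is what a Kaplan-Meier comparison needs.
- The phrase "Irrespective of the time after the index procedure" in the probable ST definition introduces a criterion with no time limit. It does not choose a clock.

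On this reading each variable has one source: event time from index, class from adjudication. Both can be reported, as Appendix II asks. An early ST of a day-45 stent can fall as late as day 45 + 30 = 75 from index. It then counts as early by class but lies outside a 30-day Kaplan-Meier rate. Those are two different quantities, and neither is wrong.

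**3. Size if an analyst nevertheless used index days for class.** The only input from the documents is 700 patients per arm (section 9.3). Everything else is assumed:

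- 5% to 15% of patients are staged, with staging days spread evenly over days 1 to 45.
- 0.5% to 1% of staged patients have an early ST of the staged stent.
- 0.1% to 0.3% have an unexplained death within 30 days of it.
- 0.2% to 0.5% have a late ST of it.

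Share of early events that cross day 30 from index:

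- Event timing uniform over 30 days: mean of min(1, d/30) over d = 1 to 45 = (15.5 + 15)/45 = 0.678.
- Front-loaded timing (exponential, mean 5 days, truncated at 30): mean of 1 − F(30 − d), with F the truncated distribution function = 0.454.

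Expected number moved per arm = 700 × staged share × event rate × crossing share:

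- Early to late ST: 700 × 0.05 × 0.005 × 0.454 = 0.08, up to 700 × 0.15 × 0.01 × 0.678 = 0.71.
- Probable to possible ST: 700 × 0.05 × 0.001 × 0.454 = 0.02, up to 700 × 0.15 × 0.003 × 0.678 = 0.21.
- Late to very late ST: crossing share = mean of d/335 = 23/335 = 0.0687 (late ST uniform over days 30 to 365). This gives 700 × 0.05 × 0.002 × 0.0687 = 0.005, up to 700 × 0.15 × 0.005 × 0.0687 = 0.04.

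All three apply only if the misreading occurs. I attach no probability to that, since the documents give no basis for one.

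**The case for a change.** The strongest case for a change is textual. The only sentence that deals with event timing under staging is in 9.6, and it points to the index date without exception. No supplied text confines it to the Kaplan-Meier axis. Appendix II does not separate index from staged implantation, and the committee's algorithm sits in a charter that is not among the documents. A short clarification would cost little, and one moved event matters in a low-count endpoint.

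The gap in the text stands. The step from the gap to a wrong result does not, because each consequence requires an analyst to discard the adjudicated class that section 12.4 provides.

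A rule counting from the stent concerned would also leave the hardest case open. An unexplained death in a patient with both index and staged stents generally cannot be tied to one of them, so it would still depend on the committee's charter. That is the only one of the three movements that reaches 5b and 5c; the other two change timing labels in 5a alone.

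**Conclusion.** No change is needed. Followed as written, the plan takes event times from the index date and ST class from committee adjudication under Appendix II, and no result is shown to change. What is missing is an explicit statement of how the two rules relate for staged stents. A sentence saying so would do no harm, but it would only record the reading the documents already favour.

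Even under the misreading, fewer than one early ST per arm would be expected to move at the top of the assumed ranges. The effect applies to both arms, with no between-arm bias shown. Primary target lesion failure at 12 months, the 4% margin and the sample of 1400 are unaffected.

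The conclusion rests on the committee classifying ST as section 12.4 directs and on its charter, not seen here, being consistent with Appendix II.

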10 SAFETY REPORTING

10.1 Serious Adverse Events (SAEs) Definitions

An AE is defined as any untoward medical occurrence, unintended disease or injury, or untoward clinical signs (including abnormal laboratory findings) in subjects, users or other persons, whether or not related to the investigational medical device.

An AE is classified as “serious” if the event:

- Led to death;
- Led to serious deterioration in the health of a patient that:
 - Resulted in a life threatening illness or injury;
 - Resulted in a permanent impairment of a body structure or a body function;
 - Required in patients hospitalization or prolongation of existing hospitalization;
 - Resulted in medical or surgical intervention to prevent permanent impairment to a body structure or a body function.
- Led to foetal distress, foetal death or a congenital abnormality or birth defect.

NOTE: Planned hospitalization for a pre-existing condition, or a procedure required by the CIP, without serious deterioration in health, is not considered a serious adverse event.

10.2 Anticipated Adverse Device Effects

Anticipated adverse device effects for both MISTENT and XIENCE are described in the Instructions For Use.

10.3 Device Malfunctions

If the investigator observes device malfunctions that led or might have led to a death or serious deterioration in health of a patient, user or other person, or has complaints with regard to defects in the medical devices, the investigator shall, within 24 hours of such observation, report such device malfunction or complaint to the device company, with a copy of the report to the sponsor. Sponsor shall be responsible to take necessary actions in response to a device malfunction to protect the safety of the trial subjects, e.g. temporary suspension of the trial. The Company shall be responsible for handling all complaints and reported device malfunctions in respect of the quality of medical devices, for determining the measures to be taken due to such observations or complaints and for ensuring that all necessary actions are taken including, but not limited to, any necessary action in connection with the recall of the medical devices or the reporting of incidents to competent authorities if deemed appropriate by the Company. Discussions regarding such device malfunction or complaints will be held between the Company and the Participating Site.

For definition refer also to Appendix II.

10.4 SAE Reporting

The investigator will monitor the occurrence of Serious Adverse Events (SAEs) for each subject during the course of the study. For the purpose of this protocol, the reporting of SAEs begins

directly after patient has signed informed consent through the last follow-up visit. If an event fulfills the criteria for SAE, then this shall be reported in the eCRF within 24 hours of the clinic study staff having become aware of this, including their judgment regarding causal relationship of the event to the trial. At the time the event is reported in the eCRF, no event-supporting source documentation needs to be sent. Event supporting source documents will be requested by the sponsor (via monitoring organization and/or CRO) for the purpose of potential clinical event adjudication and reporting purposes. All SAEs will be followed until the event has been resolved (with or without sequelae).

Sponsor is responsible for the classification of adverse events and ongoing safety evaluation of the clinical investigation and shall review the investigator's assessment of all adverse events and determine and document in writing the sponsor's determination of seriousness and relationship to the investigational device; in case of disagreement between the sponsor and the principal investigator(s), both opinions shall be reflected.

Safety reporting to the Competent Authorities and the local ECs will be in accordance with "Clinical investigation of medical devices for human subjects - Good clinical practice" (ISO 14155:2011, IDT) and the "guidelines on medical devices vigilance system" by the European Commission (MEDDEV2.12 rev 6, Dec 2009) and in compliance with local country law.

10.5 Risk Analysis

Percutaneous coronary interventions (PCI) and intravascular stenting may offer certain advantages as compared to conventional surgical techniques. In addition, coronary stenting with both BMS and DES have been performed successfully for several decades and is considered a standard treatment for coronary revascularizations. Furthermore, there is extensive clinical and commercial experience worldwide with cardiac catheterization and interventional procedures and it is expected that the procedural risks in this study and existing stenting procedure will not be significantly different. Further, since the drug-polymer coating on the MISTENT is gone within 90 days, leaving a bare metal stent, this may diminish the potential concerns regarding long-term effect on vessel healing, late and very late thrombosis, and hypersensitivity. Aside from the potential direct benefits to the patient resulting from this study, there may be benefits to future patients based upon the results of the study.

With any procedure there are risks and complications. The following is a list of known adverse events (alphabetical order) that may result from stent intervention:

COMMON - More than 10%

Angina pectoris

Bleeding or hematoma (bruising) at the access site

Pain at the catheter insertion site

Unstable angina

LESS COMMON - 2% to 9%

Acute myocardial infarction

Arrhythmias

Confidential and Proprietary

Do not distribute or reproduce without the prior written permission of ECRI.
CIP Version 2.0 – 07 March 2018

Bradycardia
Hypotension
Restenosis of the stented artery
Thrombus formation

RARE - 1% or less
Abrupt vessel closure
Allergic reaction to contrast media (dye), aspirin, heparin and Angiomax® (bivalirudin), clopidogrel bisulfate (Plavix), ticlopidine (Ticlid) Prasurgrel (Effient) or Ticagrelor (Brilinta), as prescribed
Aneurysm, pseudoaneurysm or arteriovenous fistula
Cardiac tamponade
Cerebral vascular event
Coronary artery aneurysm
Damage to the stent or injury to the artery requiring emergency heart surgery
Death
Device embolization
Dissection, perforation, or rupture of the coronary artery
Embolism (air, tissue, thrombus or device)
Hypersensitivity to cobalt-chromium
Hypersensitivity to sirolimus
Hypersensitivity to everolimus
Infection or fever
Pseudoaneurysm or fistula at the vascular access site
Stent misplacement
Stent thrombosis or occlusion
Stroke or transient ischemic attack (TIA)
Thromboembolic events
Vascular trauma

11 QUALITY CONTROL AND QUALITY ASSURANCE

11.1 Compliance to Standards and Regulations

The protocol, informed consent form and other study-related documents will be submitted to the Ethics Committee (EC) / Institutional Review Board (IRB). The study will be performed in accordance with the Declaration of Helsinki and Good Clinical Practices (GCP).

The trial will only start at a clinical site after written approval of the study has been obtained from the appropriate national EC/IRB.

11.2 Data Recording

It is the expectation of the Sponsor that all data entered into the eCRF has source documentation available at the clinical site. The site must implement processes to ensure this happens.

11.3 Quality Assurance and Monitoring

Monitoring the clinical investigation at the study site is the responsibility of the monitoring organization through trained and qualified Clinical Research Associates (CRAs).

The monitoring organization will discuss the investigator's patient enrollment prediction at the time of contracting.

Monitoring visits will be performed according to the monitoring plan. During on-site monitoring, the Informed Consent Forms will be checked and a sample of clinical data will be verified against eCRF data. Subject confidentiality will be maintained at all time. Emphasis will be on the complete reporting by the study staff of SAEs.

Each clinical site will be visited several times during the study to ensure a high degree of data quality. These site monitoring visits will be conducted to verify that the data are authentic, accurate and complete, that the safety and rights of subjects are protected, that the study is conducted according to the protocol, and that any other study agreements, GCP and all applicable regulatory requirements are met. The investigator and the head of the medical institution (where applicable) agree to allow the CRA direct access to all relevant documents. It is important that the investigator and the study staff are available during the monitoring visit and possible audits and that sufficient time is devoted to the process. Findings from the review and source documents will be discussed with the investigator. The number of monitoring visits will depend on Key Performance Indicators (KPI) derived from data management.

Remote site monitoring will also be performed to ensure complete quality study data and patient adherence to the protocol. On a regular basis, the monitoring organization will contact each site to discuss the progress of the study with respect to patient enrollment, timely attendance of patients to their follow-up visits and other relevant study aspects such as data query resolution.

Each participating clinic will receive a close-out visit to resolve any outstanding issues and to perform the final source data verification.

There will be regular teleconferences between the Sponsor and the monitoring organization to discuss site management issues.

11.4 Quality Assurance and Data management

The data collection will be performed through an electronic CRF (eCRF). The investigator or an authorized member of the investigational team must sign all completed eCRFs that require a signature by using an electronic signature (a password will be provided by the data management center at the start of the study).

Clinical data management will be performed in accordance with data cleaning procedures. This is applicable for data recorded in the eCRF as well as for data from other sources (e.g. angiographies, ECGs, etc.). Appropriate computer edit programs will be run to verify the accuracy of the database. The investigator will be queried on incomplete, inconsistent or missing data.

